6.2 Protocol Administration

6.2.1 Dose Specifications

Note: Intensity Modulated RT (IMRT) Is Not Allowed without approval of PI.

6.2.1.1 Stereotactic Targeting and Treatment

The term "stereotactic" for the purposes of this protocol implies the targeting, planning, and directing of therapy using beams of radiation along any trajectory in 3-D space toward a target of known 3-D coordinates. This differs from conventional radiation therapy in which therapy is directed toward skin marks or bony landmarks that are indirectly referenced to the tumor. This protocol will require treatments to be conducted with the use of a fixed 3-D coordinate system defined by fiducials. The coordinate system defined by the fiducials should be directly related to the radiation producing device (e.g., couch and gantry) in a reproducible and secure fashion. Capability should exist to define the position of targets within the patient according to this same 3-D coordinate system. As such, the patient is set up for each treatment with the intention of directing the radiation toward an isocenter or target according to the known 3-D coordinates as determined in the process of treatment planning. The nature of the fiducials themselves may include radio-opaque markers or rods placed at known locations in a frame or fixed structure adjacent to the patient as well as use of the tumor itself as a fiducial (e.g. acquiring tomographic views of the tumor simultaneously with the treatment). Metallic "seeds" placed within the tumor will not

generally be allowed to constitute a fiducial unless the site employing this technique provides satisfactory validation to the Study Chair indicating no seed migration and reproducibility of target positioning from treatment to treatment and obtains permission in writing from the Study Committee (Principal Investigator and Co-Chairs) prior to treatment.

6.2.1.2 Dose Fractionation

Patients will receive 1 (30 Gy) or 3 (20 Gy) fractions of radiation. A minimum of 40 hours and a maximum of 8 days should separate each treatment. No more than 2 fractions will be delivered per week (7 consecutive days). The dose for all patients per fraction will be to the prescription line at the edge of the PTV. If giving 3 fractions, treatment will be delivered as above over 8-24 days for a total of 60 Gy. Overall treatment time for one fraction is one day, for three fractions is 8-24 days. Treatment may start within 4 weeks after registration.

6.2.1.3 *Premedications*

Unless contraindicated, it is recommended that all patients receive corticosteroid premedication (e.g. Decadron 4 mg p.o. in a single dose, or equivalent) 15-60 minutes prior to each of the treatment for the intended purpose of modulating immediate pulmonary inflammatory effects. Analgesic premedication to avoid general discomfort during long treatment durations also is recommended when appropriate.

6.2.2 Technical Factors

6.2.2.1 Physical Factors

Only photon (x-ray) beams produced by linear accelerators, betatrons, or microtron accelerators with photon energies 6-23 MV will be allowed. Cobalt-60 and charged particle beams (including electrons, protons, and heavier ions) are not allowed. Photon beam energies greater than 6 MV but not more than 23 MV will only be allowed for a limited number (\leq 2) beams that must travel more than a cumulative distance of 10 cm through soft tissue (not lung) to reach the isocenter.

6.2.2.2 Minimum Field Aperture (Field Size) Dimension

Due to uncertainties in beam commissioning resulting from electronic disequilibrium within small beam apertures, a minimum field dimension of 3.5 cm is required for any field used for treatment delivery. It is understood that this may exceed the technical requirements listed in Section 6.4 for small lesions (< 2.5 cm axial GTV dimension or < 1.5 cm cranio-caudal GTV dimension). In such cases, the prescription dose is still prescribed to the edge of the defined PTV. This minimum field dimension does not apply to centers using tomotherapy or multiple pencil beam delivery systems.

6.2.2.3 Dose Verification at Treatment

Personal dosimeter measurements (e.g. diode, TLD, etc.) may be obtained for surface dose verification for accessible beams as per institutional preference. This information is not required by the protocol.

6.2.3 Localization, Simulation, and Immobilization

6.2.3.1 Patient Positioning

Patients will be positioned in a stable position capable of allowing accurate reproducibility of the target position from treatment to treatment. Positions uncomfortable for the patient should be avoided so as to prevent uncontrolled movement during treatments.

It is very important that a rigid immobilization device be prepared in the CT Simulator to ensure reproducible set up of the patient during his/her treatment. Selection of an appropriate immobilization device will be done after consulting with the physician who may elect to use one or many such immobilization devices together [e.g. BodyFix along with vaclock system etc.] for a particular patient.

6.2.3.2 Internal Organ Motion/ Tumor Localization

Patients will undergo simulation using a respiratory gating technique which synchronizes radiation delivery to an individual's breathing cycle. Image acquisition takes place only during a pre-specified portion of the respiratory cycle (maximum inhalation or end-expiration) thus helping to determine margins needed to encompass tumor motion throughout the breathing cycle. Respiratory gating will be used only for determination of ITV and is not used for actual treatment delivery.

Due to significant intrafraction motion of the tumor, it is proposed to use respiratory gating to determine the maximum extent of tumor motion by taking at least 2 additional scan sets/series viz. exhale and inhale phase. The gated CT image set can cover a much smaller superior-inferior extent. These limits will be defined by the radiation oncologist and are usually 2 cm beyond the GTV limits defined earlier utilizing the topogram/scout view. The patient is now instructed to breathe in a reproducible manner. Using the RPM system, appropriate threshold levels are then generated for phase based gating enabling gated CTdata acquisition in the inhale and exhale stage. It is very important to ensure that the couch parameters and the patient position remain unchanged in all the three series acquisitions [normal breathing, exhale & inhale state]. The necessary gating parameters, as well as the other series identification information will be recorded in the conventional free-breathing gating sheet in use for such patients and will be attached with the patient's chart. It is important to remember that the above procedure mentioned for determining the ITV is strictly true only for the single-slice CT scanner allowing prospective gating scans.

In some lung SBRT cases, it may not be possible to use RPM gating system to acquire the additional scans in inhale and exhale phase as the patient may be having very shallow breathing pattern. In those type of circumstances, it might be easier to acquire a cone beam CT scan (CBCT). The CBCT will then be co-registered with regular normal breathing CT simulation image series and will be used instead of the inhale and exhale image series obtained through respiratory gating. Cone beam CT images will be taken just prior to delivery of each radiation fraction while the patient is in the treatment position on the linear accelerator. These CT images can be compared with the original treatment planning CT and adjustments can be made as necessary to precisely conform treatment delivery to the original plan. This process may be repeated during RT more than once per physician discretion.

Cone beam CT will give an idea about the average tumor motion as the CBCT image is reconstructed using 550+ planar images acquired in around 1 minute. Such an image can either be acquired directly using CBCT application or can also be generated through the regular process of 3D/3D match. Please note that prior to acquiring these CBCT images, the patient will be repositioned on the Trilogy couch exactly the same way as it was on the CT Simulator. The reconstructed CT images can then be imported and registered in Eclipse. Since OBI station is on its own network, a direct transfer of the patient files which are in D:\patient\MR# directory is not possible but Compact disks [CDR] can be used to burn the images. Virus free flash drives may also be used for this purpose.

Tumor localization methods are constantly evolving. As other accepted methods of tumor localization become available, including image based and implantable fiducial marker based methods, these may be substituted at the PI's discretion.

6.2.4 Treatment Planning/Target Volumes

6.2.4.1 Image Acquisition

Computed Tomography (CT) will be the primary image platform for targeting and treatment planning. The planning CT scans must allow simultaneous view of the patient anatomy and fiducial system for stereotactic targeting. If IV contrast dye is used, then 1) 2 sets of images one without the dye and one with the dye should be done or 2) a bulk density must be defined in the treatment planning system for the region of dye. Axial acquisitions with gantry 0 degrees will be required

with spacing \leq 3.0 mm between scans. Images will be digitally transferred to the treatment planning computers.

Once images have been transferred to the planning system, the target lesion and surrounding normal tissue structures will be outlined by the treating physician. The target will generally be drawn using CT pulmonary windows; however, soft tissue windows with contrast may be used to avoid inclusion of adjacent vessels, atelectasis, or mediastinal or chest wall structures within the GTV. The Gross Tumor Volume (GTV) is defined as the visible tumor on CT. No margin will be added for presumed microscopic extension. The Clinical Target Volume (CTV) and GTV are thus identical.

There are 2 acceptable methods to define the PTV depending on the method of CT simulation:

- (a) Conventional (helical) CT-simulation (non-4DCT): The PTV will include the GTV plus an additional 0.5 cm margin in the axial plane and 1.0 cm margin in the longitudinal plane (craniocaudal).
- (b) 4D CT-simulation: An internal target volume (ITV) around the GTV, accounting for tumor motion may be defined from the 4D CT dataset. The PTV will include the ITV plus an additional 0.5 cm margin uniformly applied to the ITV.

These margins will be used at all institutions, even if a particular institution uses equipment or techniques felt to be more accurate.

6.2.4.2 Dosimetry

Three-dimensional coplanar or non-coplanar beam arrangements will be custom designed for each case to deliver highly conformal prescription dose distributions. Non-opposing, non-coplanar beams are preferable. Typically, 7-10 beams of radiation will be used with roughly equal weighting. Generally, more beams are used for larger lesion sizes. When static beams are used, a minimum of 7 non-opposing beams should be used. For arc rotation techniques, a minimum of 340 degrees (cumulative for all beams) should be utilized. For this protocol, the isocenter is defined as the common point of gantry, collimator, and couch rotation for the treatment unit. Field aperture size and shape should correspond nearly identically to the projection of the PTV along a beam's eye view (i.e. no additional "margin" for dose build up at the edges of the blocks or MLC jaws beyond the PTV). The only exception will be when observing the minimum field dimension of 3.5 cm when treating small lesions. As such, prescription lines covering the PTV will

typically be the 60-90% line (rather than 95-100%); however, higher isodoses (hotspots) must be manipulated to occur within the target and not in adjacent normal tissue. The isocenter in stereotactic coordinates will be determined from system fiducials (or directly from the tumor) and translated to the treatment record.

The treatment dose plan will be made up of multiple static beams or arcs as described above. The plan should be normalized to a defined point corresponding closely to the center of mass of the PTV (COM_{DTV}). Typically, this point will be the isocenter of the beam rotation; however, it is not a protocol requirement for this point to be the isocenter. Regardless, the point identified as COM_{PTV} must have defined stereotactic coordinates and receive 100% of the normalized dose. Because the beam apertures coincide nearly directly with the edge of the PTV (little or no added margin), the external border of the PTV will be covered by a lower isodose surface than usually used in conventional radiotherapy planning, typically around 80% but ranging from 60-90%. The prescription dose of 60 Gy in three fractions will be delivered to the margin of the PTV and fulfill the requirements below. As such, a "hot spot" will exist within the PTV centrally at the COM_{PTV} with a magnitude of 60 Gy times the reciprocal of the chosen prescription isodose line (i.e., 60-90%).

Tissue heterogeneity corrections **will not be used for the patient's treatment.** For purposes of dose planning and calculation of monitor units for actual treatment, all tissues within the body, including lung, will be assumed to have unit (water) density (no correction for tissue heterogeneity).

Once a treatment plan has been approved, an additional treatment plan will be generated with inhomogeneity correction ON. However, this plan will be altered in such a way that it carries the monitor units of the inhomogeneity OFF treatment plan. The dose to various critical structures and dosimetric indices will be recorded for documentation purposes in another worksheet which will have all the parameters as specified earlier as well as following parameters [volume of PTV receiving 60 Gy {or 30 Gy in case of single dose SBRT} or more [V₆₀] and D₉₅]. The exact inhomogeneity correction algorithm to be used for these patients will be the same which is being used for rest of the patients being treated at RPCI. Of note, the calculation grid utilized should be as small as possible.

Successful treatment planning will require accomplishment of all of the following criteria:

1) Normalization

The treatment plan should be normalized such that 100% corresponds to the center of mass of the PTV (COM_{PTV}). This point will typically also correspond (but is not required to correspond) to the isocenter of the treatment beams.

2) Prescription Isodose Surface Coverage

The prescription isodose surface will be chosen such that 95% of the target volume (PTV) is conformally covered by the prescription isodose surface (i.e., 20 Gy per fraction = 60 Gy total; 30 Gy single fraction = 30 Gy total)), and 99% of the target volume (PTV) receives a minimum of 90% of the prescription dose (i.e., 18 Gy per fraction = 54 Gy total for 3 fraction regimen; 27 Gy for single fraction regimen).

3) Target Dose Heterogeneity

The prescription isodose surface selected in number 2 (above) must be $\ge 60\%$ of the dose at the center of mass of the PTV (COM_{PTV}) and $\le 90\%$ of the dose at the center of mass of the PTV (COM_{PTV}). The COM_{PTV} corresponds to the normalization point (100%) of the plan as noted in 1) above.

4) High Dose Spillage

a) Location

Any dose greater than 105% of the prescription dose (> 21Gy per fraction = 63 Gy total for 3 fraction regimen; >31.5 Gy for single fraction) should occur primarily within the PTV itself and not within the normal tissues outside of the PTV. Therefore, the cumulative volume of all tissue outside of the PTV receiving a dose greater than 105% of prescription dose (> 21Gy per fraction = 63 Gy total for 3 fraction regimen; >31.5 Gy for single fraction) should be no more than 15% of the PTV volume.

b) Volume

Conformality of PTV coverage will be judged such that the ratio of the volume of the prescription isodose meeting criteria 1) through 4) to the volume of the PTV is ideally < 1.2 (See table below). These criteria will not be required to be met in treating very small tumors (< 2.5 cm axial GTV dimension or < 1.5 cm cranio-caudal GTV dimension) where the required minimum field size of 3.5 cm results in the inability to meet a conformality ratio of 1.2.

5) Low Dose Spillage

The falloff gradient beyond the PTV extending into normal tissue structures must be rapid in all directions and meet the following criteria:

a) Location

The maximum total dose over all 3 fractions in Gray (Gy) to any point 2 cm or greater away from the PTV in any direction be no greater than D_{2cm} where D_{2cm} is given by the table below.

b) Volume

The ratio of the volume of 50% of the prescription dose (10 Gy per fraction = 30 Gy total for 3 fraction regimen; 15 Gy for single fraction) isodose to the volume of the PTV must be no greater than $R_{50\%}$ where $R_{50\%}$ is given by the table below.

Maximum	Rat	io of	Ratio of 50%		Maximum Dose		Perc	PTV	
PTV	Prescription		Prescription		2cm from PTV in		Lung receiving		volume
Dimension	Isodose	Volume	Isodose	Volume	any Dir	ection (in	20 Ğy	total or	(in cc)
(cm)	to F	νTV	to PTV	′ (R _{50%})		Gy)	more	V20 (%)	· · /
	Devi	ation	Devi	ation	Dev	viation	Dev	viation	
	None	Minor	None	Minor	None	Minor	None	Minor	
2.0	<1.2	1.2 –	< 3.9	3.9 –	< 28.1	28.1 –	< 10	10 - 15	1.8
		1.4		4.1		30.1			
2.5	<1.2	1.2 –	< 3.9	3.9 –	< 28.1	28.1 –	< 10	10 –	3.8
		1.4		4.1		30.1		15	
3.0	<1.2	1.2 –	< 3.9	3.9 –	< 28.1	28.1 –	< 10	10 - 15	7.4
		1.4		4.1		30.1			
3.5	<1.2	1.2 –	< 3.9	3.9 –	< 28.1	28.1 –	< 10	10 —	13.2
		1.4		4.1		30.1		15	
4.0	<1.2	1.2 –	< 3.8	3.8 –	< 30.4	30.4 -	< 10	10 –	21.9
		1.4		4.0		32.4		15	
4.5	<1.2	1.2 –	< 3.7	3.7 –	< 32.7	32.7 –	< 10	10 —	33.8
		1.4		3.9		34.7		15	
5.0	<1.2	1.2 –	< 3.6	3.6 –	< 35.1	35.1 –	< 10	10 –	49.6
		1.4		3.8		37.1		15	
5.5	<1.2	1.2 –	< 3.5	3.5 –	< 37.4	37.4 –	< 10	10 –	69.9
		1.4		3.7		39.4		15	
6.0	<1.2	1.2 –	< 3.3	3.3 –	< 39.7	39.7 –	< 10	10 –	95.1
		1.4		3.5		41.7		15	
6.5	<1.2	1.2 –	< 3.1	3.1 –	< 42.0	42.0 –	< 10	10 –	125.8
		1.4		3.3		44.0		15	
7.0	<1.2	1.2 –	< 2.9	2.9 –	< 44.3	44.3 –	< 10	10 –	162.6
		1.4		3.1		46.3		15	

TABLE 1: Conformality Criteria and Lung Radiation Limits

7.5	<1.2	1.2 –	< 2.7	2.7 –	< 46.6	46.6 –	< 10	10 –	
		1.4		2.9		48.6		15	
8.0	<1.2	1.2 –	< 2.5	2.5 –	< 48.9	48.9 –	< 10	10 –	
		1.4		2.7		50.9		15	

Note 1: For values of PTV dimension or volume not specified, linear interpolation between table entries is required.

Note 2: Protocol deviations greater than listed here as 'minor' will require approval of the treating physician or PI prior to treatment.

Note 3: These limits will apply to both treatment arms.

 Respect all critical organ dose-volume limits listed in Section 6.5.1 below.

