6.2.5 Critical Structures

6.2.5.1 Critical Organ Dose-Volume Limits

The following table lists maximum dose limits to a point or volume within several critical organs. These are absolute limits, and treatment delivery that exceeds these limits will constitute a major protocol violation.

The limits for 20Gy x 3 are taken from RTOG 0236 and were formulated with the approval of the RTOG study committee (Principal Investigators and Co-Chairs) including [name], international authority on radiobiology and radiotolerance, using known tolerance data, radiobiological conversion models, norms used in current practice at academic centers,¹⁶⁻²² and the experience of several years of irradiation using these large fractions at Indiana University^{26,30,31} and centers in Sweden,^{24,25,27} Germany, and Japan. With the exception of the spinal cord limit which is conservatively set from experience with irradiation of vertebral body metastases, the dose limits for 30 Gy were scaled from the limits at 20 Gy per fraction. However, even for the 30 Gy arm, we will endeavor to meet the single fraction dose limits of the 20 Gy arm.

In order to verify each of these limits, the organs must be contoured such that appropriate dose volume histograms can be generated. Instruction for the contouring of these organs will follow below.

TABLE 2a: DOSE LIMITS TO CRITICAL STRUCTURES for 20 Gy x3

Organ		20 Gy x 3 Arm
	Volume	
Spinal Cord	Any point	18 Gy (6 Gy
		per fraction)
Esophagus	Any point	27 Gy (9 Gy
		per fraction)
Ipsilateral	Any point	24 Gy (8 Gy
Brachial Plexus		per fraction)
Heart	Any point	30 Gy (10 Gy
		per fraction)
Trachea and	Any point	30 Gy (10 Gy
Ipsilateral		per fraction)
Bronchus		
Whole Lung	(See table in	(See table
(Right & Left)	Section 6.4.2)	below)

TABLE 2b: DOSE LIMITS TO CRITICAL STRUCTURES for 30 Gy x1

Serial Tissue		Volume Max	Max Point Dose	Endpoint (≥Grade
	Volume	(Gy)	(Gy)	3)
Spinal Cord	<0.35 cc	10 Gy	14 Gy	myelitis
	<1.2 cc	7 Gy		
Esophagus*	<5 cc	11.9 Gy	15.4 Gy	stenosis/fistula
Brachial Plexus	<3 cc	14 Gy	17.5 Gy	neuropathy
Heart/Pericardi	<15 cc	16 Gy	22 Gy	pericarditis
um				
Great vessels	<10 cc	31 Gy	37 Gy	aneurysm
Trachea and	<4 cc	10.5 Gy	20.2 Gy	stenosis/fistula
Large				
Bronchus*				
Rib	<1 cc	22 Gy	30 Gy	Pain or fracture
Skin	<10 cc	23 Gy	26 Gy	ulceration
Stomach	<10 cc	11.2 Gy	12.4 Gy	ulceration/fistula
Parallel Tissue		Critical Volume		Endpoint (≥Grade
	Critical	Dose Max (Gy)		3)
	Volume			
	(cc)			

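### The 2 cm point-dose limit (D2cm) is a three-fraction total in Gy but is applied unchanged to the 30 Gy single-fraction arm, where it has almost no force

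*Combined protocol and SAP*

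**What the plan says.** Section 6.2.4.2 lists criteria that every treatment plan has to meet. Criterion 5 concerns low-dose spillage and says that the falloff outside the PTV "must be rapid in all directions and meet the following criteria". Part (a) states the cap in these terms: "The maximum total dose over all 3 fractions in Gray (Gy) to any point 2 cm or greater away from the PTV" may not exceed D2cm, which is read from Table 1 by PTV dimension. Table 1 has one D2cm column, in Gy, with a no-deviation limit and a minor-deviation band 2 Gy wide in each row. Beneath it stands "Note 3: These limits will apply to both treatment arms".

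Part (b), the R50% ratio, is specified separately for each arm: "10 Gy per fraction = 30 Gy total for 3 fraction regimen; 15 Gy for single fraction". Criteria 2 and 4a do the same, with 54 or 27 Gy for 90% of prescription and 63 or 31.5 Gy for 105%.

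Section 6.2.5.2.7 makes the 2 cm maximum a QA requirement, and Section 6.2.7.1 takes its deviation grades from the Section 6.2.4 table. Note 2 asks for approval by the treating physician or the PI when a plan goes beyond a minor deviation. Section 6.2.5.1 says that the 30 Gy limits, spinal cord excepted, were scaled from those at 20 Gy per fraction. That statement concerns the organ limits in Tables 2a and 2b and does not reach Table 1.

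**The concern.** A cap on dose 2 cm outside the target works only if it sits well below the prescription. The D2cm figures are set against a 60 Gy total. Carried over in absolute Gy to an arm that prescribes 30 Gy, the same figures are twice as large relative to the prescription, and a plan would have to be grossly abnormal to break them.

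At stake is the meaning of the compliance grade. A plan graded free of deviation on this item has passed a real test in one arm and close to none in the other, and the approval step in Note 2 is unlikely to be reached for this item in the 30 Gy arm.

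**Working it through.** **Inputs.** The D2cm limits come from Table 1 and the prescriptions (60 Gy and 30 Gy) from criterion 2. The prescription line, from Section 6.2.4.2, is "typically around 80% but ranging from 60-90" per cent. The margins come from Section 6.2.4.1 and the 5 cm size limit from Section 3.1.

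**Figures the plan does scale.** 0.90 x 60 = 54 and 0.90 x 30 = 27 Gy; 1.05 x 60 = 63 and 1.05 x 30 = 31.5 Gy; 0.50 x 60 = 30 and 0.50 x 30 = 15 Gy. All match the text. The plan gives no derivation or percentage for D2cm, so there is none to reproduce.

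**D2cm as a share of prescription** (limit / 60 and limit / 30):

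| PTV dimension (cm) | No-deviation limit (Gy) | 60 Gy arm | 30 Gy arm |
|---|---|---|---|
| 2.0 to 3.5 | 28.1 | 47% | 94% |
| 4.0 | 30.4 | 51% | 101% |
| 4.5 | 32.7 | 55% | 109% |
| 5.0 | 35.1 | 59% | 117% |
| 6.0 | 39.7 | 66% | 132% |
| 7.0 | 44.3 | 74% | 148% |

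The minor-deviation ceiling exceeds 30 Gy in every row: 30.1 / 30 = 100.3% up to 3.5 cm, 32.4 / 30 = 108% at 4.0 cm and 46.3 / 30 = 154% at 7.0 cm.

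**Which rows are reachable.** With helical CT margins, a 5 cm tumour gives at most 5 + 2 x 1.0 = 7.0 cm. A tumour only 2 cm long craniocaudally already gives 2 + 2 x 1.0 = 4.0 cm, where the limit passes 100% of prescription.

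**Against the arm's own thresholds.** From the 4.5 cm row the low-dose limit (32.7 Gy) is above the 31.5 Gy that criterion 4a treats as high-dose spillage. The dose at the PTV centre is the prescription divided by the isodose line: 30 / 0.9 = 33.3 Gy, 30 / 0.8 = 37.5 Gy, 30 / 0.6 = 50 Gy. At the typical 80% line, the 6.0 cm limit is 39.7 / 37.5 = 106% of the centre dose, so the dose allowed 2 cm outside the target exceeds the dose at its centre. In the 60 Gy arm the same ratio is 39.7 / 75 = 53%.

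**What R50% still does.** Assume equal-volume spheres with the Table 1 PTV volumes V and r(V) = (3V / 4π)^(1/3). At the no-deviation limit the 15 Gy surface then lies beyond the PTV by r(3.8 x 21.9) − r(21.9) = 0.97 cm at 4.0 cm, r(3.6 x 49.6) − r(49.6) = 1.21 cm at 5.0 cm and r(2.9 x 162.6) − r(162.6) = 1.44 cm at 7.0 cm. These are mean distances under a model. They do not bound the dose in any one direction.

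**Candidate scalings for the 28.1 Gy rows.**
- Same percentage of prescription: 28.1 x 30 / 60 = 14.05 Gy.
- Per fraction: 28.1 / 3 = 9.4 Gy.
- Table 2b over Table 2a point limits: esophagus 15.4 / 27 = 0.570, trachea and bronchus 20.2 / 30 = 0.673, brachial plexus 17.5 / 24 = 0.729, heart 22 / 30 = 0.733. Applied to 28.1 these give 16.0 to 20.6 Gy. The cord is left out because it was not scaled.

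Every candidate is far below 28.1 Gy.

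**The case against.** The strongest reply is that little depends on this one item. Single-fraction plans must still meet R50% at 15 Gy, the 105% rule, the prescription-isodose ratio and the requirement of rapid falloff in every direction. For static fields "a minimum of 7 non-opposing beams should be used", typically 7 to 10 with roughly equal weighting, or at least 340 degrees of arc. "Intensity Modulated RT (IMRT) Is Not Allowed without approval of PI" also applies. Table 2b sets organ limits, of which Section 6.2.5.1 says "These are absolute limits, and treatment delivery that exceeds these limits will constitute a major protocol violation", and the same section aims to meet the 20 Gy arm's per-fraction organ limits in the 30 Gy arm too. Approval under Note 2 can come from the treating physician, so the lost approval step is a modest one. From the 4.0 cm row up, a halved D2cm (15.2 Gy or more) lies above 15 Gy, while the modelled mean 15 Gy surface is already inside 2 cm. No document shows a plan that would pass everything else and fail a rescaled cap.

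Most of this stands, and it limits the consequence. It does not make the tabulated figures workable. A mean distance or an isodose volume cannot cap a directional maximum, and that is what D2cm is for.

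A reader might infer four stronger things that the documents do not support:

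- *That lung is unprotected in the 30 Gy arm.* Lung keeps V20 in Table 1 and two critical-volume limits in Table 2b (1500 cc at 7 Gy, 1000 cc at 7.4 Gy), and Table 2b treats it as a parallel tissue. It lacks only a point cap.
- *That lung V20 is wrong in the same way.* It is also unscaled (20 / 60 = 33% and 20 / 30 = 67% of prescription), but it is an absolute lung-dose measure that still constrains a 30 Gy plan.
- *That the toxicity comparison or the power is affected.* The analysis in Section 12.0 does not use deviation status.
- *That halving is the intended value.* The documents state no scaling for D2cm.

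**Conclusion.** The point holds and should be fixed. For PTVs of 2.0 to 7.0 cm the no-deviation D2cm limit in the 30 Gy arm runs from 94% to 148% of prescription. It cannot serve there as a low-dose spillage limit.

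The loss is one numerical check in one arm: a point cap 2 cm or more from the PTV in tissue with no point limit of its own, namely lung parenchyma and non-rib chest wall. With the other controls in place, the practical safety effect is confined to directional outliers.

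The conclusion rests on reading Note 3 as covering the D2cm column, which is its plain meaning. If criterion 5a is read instead as binding only the three-fraction arm, it conflicts with Note 3 and leaves the 30 Gy arm with no D2cm limit, and the remedy is the same. The upper figure of 148% assumes helical CT margins. Table 1 continues to 8.0 cm, where 48.9 / 30 = 163%, and a 4D-CT target volume with large motion could reach those rows.

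**What to change.** Amend criterion 5a, the D2cm column of Table 1 and Note 3 to give a separate single-fraction D2cm. As a provisional default, use the same percentage of prescription as the 60 Gy arm, in line with criteria 2, 4a and 5b:

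| PTV dimension (cm) | No-deviation limit (Gy) | Minor ceiling (Gy) |
|---|---|---|
| up to 3.5 | 14.05 | 15.05 |
| 4.0 | 15.2 | 16.2 |
| 5.0 | 17.55 | 18.55 |
| 7.0 | 22.15 | 23.15 |

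The remaining rows are halved likewise. Radiation oncology should confirm the final values, since the candidate scalings for the smallest PTVs span 9.4 to 20.6 Gy. Note 3 should also say that lung V20 carries over unchanged, so that this is explicit. D2cm should be reported by arm as a percentage of prescription.

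The cost is an amendment to one criterion, one column and one note. The 2 cm structure and its maximum dose are already required, so past 30 Gy plans can be regraded wherever that value was recorded. The downside is that some may be reclassified as deviations. The documents do not say how many patients remain to be planned, so the prospective benefit cannot be sized.
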